recovery and met with a clinical psychologist for motivational interviewing (MI) during IPR to discuss patients' readiness to change, confidence in using CPAP and coping techniques to adjust to CPAP use (see Table II). The 30-minute face-to-face MI sessions occurred within one week of starting auto-adjusting CPAP. The MI session were focused on building motivation to use CPAP and alter the subject's decisional balance about using CPAP as it relates to patient-specific goals. To improve support, the adherence program included nightly visits by respiratory therapists during IPR to improve self-efficacy with CPAP and tailored written feedback prior to discharge from the IPR unit detailing CPAP download data, adjustments made during IPR and goals and barriers for CPAP use. Phone calls were also made weekly for one month after discharge from the IPR unit to encourage CPAP use and troubleshoot any device or mask problems.

Efficacy Measures

The National Institutes of Health Stroke scale (NIHSS; range, 0 to 42; higher scores indicate greater neurologic impairment) scores were obtained in-person on enrollment and at 90 ± 7 days from enrollment. The Functional Independence measure (FIM) scores were obtained as part of routine clinical care. The FIM included a motor and cognitive component (motor range, 13-91; cognitive range, 5 to 35; lower scores indicate greater functional disability). The admission FIM scores were obtained in-person by rehabilitation nurses and therapists upon admission to the IPR unit and follow-up FIM scores were obtained as part of routine clinical care through phone interview by IT Health Track, Inc., between 3 and 4 months from IPR unit discharge (mean 106 days); telephone response rates are approximately 60%.

Statistical Analyses

We compared baseline demographics, stroke severity and rehabilitation characteristics by adherence, using t-tests and Chi-squared tests as appropriate. To evaluate for predictors of adherence (Table III), we performed logistic regression, adjusting for baseline demographic covariates determined *a priori* including age (≥ 65 years), race/ethnicity (White versus non-White or Hispanic), sex, obesity (body mass index ≥ 30 kg/m²), baseline NIHSS score ≥ 5 and inpatient rehabilitation length of stay (weeks). As those with aphasia were noted to be adherent to CPAP, we added this stroke characteristic into separate models post-hoc.

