We examined for differences in baseline, 3-month and changes between baseline and 3- months in NIHSS, motor FIM and cognitive FIM by CPAP adherence using the t-test with unequal variances (Table IV). We also evaluated for association of CPAP adherence with 3-month NIHSS and cognitive FIM change using linear regression in models adjusting for age ≥ 65 years, sex, race/ethnicity, body mass index ≥ 30 , and baseline NIHSS score at study enrollment (Table IV). Finally, we evaluated the proportion of adherent and non-adherent participants who had improvement in the cognitive FIM and NIHSS, which was greater than the mean improvement among the entire sample: ≥ 7 for cognitive FIM improvement and ≥ 4 for NIHSS improvement (Table V).

Table I. Main Selection Criteria

Inclusion Criteria

Informed consent

Acute ischemic stroke or intraparenchymal hemorrhage

Age \geq 18 years

Admission to inpatient stroke rehabilitation unit at Harborview Medical Center and the University of Washington Medical Center

Exclusion Criteria

Stroke related to bleeding disorder, substance abuse, tumor, vascular malformation, trauma or other secondary cause

Active CPAP use at time of enrollment

Advanced congestive heart failure (New York Heart Association class 3 or 4)

Requiring supplemental oxygen or nasogastric feeding tube

Participation in another research outcome study

Table II. Motivational Interviewing Data Form

Subject's understanding of stroke and sleep apnea:

- Subject's readiness to change:
- □Pre-contemplation
- □Contemplation
- □Preparation
- \Box Action
- □Maintenance

Any small achievable subgoals:

 \Box YES \Box NO

Subject's reason for using CPAP:

□Stroke prevention

□Stroke recovery

□Sleep improvement

 $\Box Other$

Subject's reason for not using CPAP:

□Claustrophobia

□Anxiety

□Sleep disturbance

 \Box Mask fit or leak problems

□Device problems

 $\Box Other$

On a scale of 1-10, how important do you think it is for you to treat sleep apnea and use the

CPAP device?

On a scale of 1-10, how confident are you in your ability to use the CPAP device from now until the next time we meet?

Table III. Baseline factors associated with 3-month CPAP adherence, odds ratio (95% confidence interval)*

*All models included age, sex, obesity and weeks on inpatient rehabilitation. Model 1 additionally included race and baseline NIHSS \geq 5; model 2 for race and aphasia; model 3 for race, aphasia and baseline NIHSS \geq 5.

	Model 1	Model 2	Model 3

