White race	10.9 (1.7, 701)	3.7 (0.7, 19.8)	8.2 (1.1, 62.3)
Aphasia		12.9 (1.3, 129)	8.0 (0.7, 87.7)
NIHSS≥5	14.9 (1.9, 115.7)		10.6 (1.2, 92.6)

	Adherent, mean (SD)		Non-adherent, mean (SD)			P-value*		
	Baseline	3-months	Change	Baseline	3-months	Change	Unadjusted	Adjusted
Motor FIM†	48.5 (11.2)	79.7 (12.1)	31.2 (15.7)	47.3 (17.6)	77.5 (10.8)	30.2 (13.2)	0.83	0.65
Cognitive FIM†	24.1 (6.9)	32.4 (3.7)	8.2 (6.5)	28.5 (3.9)	33.1 (2.4)	4.6 (3.0)	0.03	0.02
NIHSS ‡	6.5 (4.3)	2.7 (3.1)	-3.8 (2.6)	4.1 (2.2)	2.6 (2.6)	-1.6 (2.2)	0.003	0.03

Table IV. Improvement in cognitive FIM and NIHSS associated with CPAP adherence

CPAP indicates continuous positive airway pressure; SD, standard deviation; NIHSS, National Institutes of Health Stroke Scale; Cognitive FIM, cognitive component of Functional Independence measure

* Difference between mean changes in outcome between adherent and non-adherent patients: unadjusted using t-test with unequal variances and adjusted for age, sex, body mass index, race and baseline NIHSS using linear regression

† n=22 adherent group and n=12 non-adherent

‡ n=30 adherent group and n=19 non-adherent

Table V. Improvement in cognitive FIM and NIHSS associated with CPAP adherence

Patient characteristics	Adherent	Non-adherent	P -value
Cognitive FIM improvement ≥ 7, n (%)*	10 (45)	3 (25)	0.24
NIHSS improvement \geq 4, n (%) [†]	16 (53)	3 (16)	0.01

* n=22 adherent group and n=12 non-adherent

† n=30 adherent group and n=19 non-adherent

REFERENCES

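### Table V compares crude responder proportions although non-adherers started nearer the best end of both scales, so its NIHSS P=0.01 overstates the evidence

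*Combined protocol and SAP*

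**What the plan says.** The last sentence of Statistical Analyses describes Table V: "we evaluated the proportion of adherent and non-adherent participants who had improvement in the cognitive FIM and NIHSS", where improvement means at least 7 points on cognitive FIM or at least 4 on NIHSS. It names no covariate and no test. Chi-squared appears only earlier in that section, for comparing baseline characteristics ("using t-tests and Chi-squared tests as appropriate"). No significance level is given anywhere.

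Table V prints one P-value per row and has no footnote on adjustment:
- NIHSS: 16 (53%) adherent against 3 (16%) non-adherent, P=0.01 ("n=30 adherent group and n=19 non-adherent").
- Cognitive FIM: 10 (45%) against 3 (25%), P=0.24 ("n=22 adherent group and n=12 non-adherent").

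Table IV does adjust, for mean change only. Its footnote says the comparison is "adjusted for age, sex, body mass index, race and baseline NIHSS using linear regression". Baseline cognitive FIM is not among those covariates.

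Efficacy Measures gives the scale limits: NIHSS "range, 0 to 42; higher scores indicate greater neurologic impairment", and FIM "cognitive range, 5 to 35; lower scores indicate greater functional disability".

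**The concern.** A fixed-change responder definition gives patients with milder deficits less chance to respond. Nobody who starts at NIHSS 3 or below can improve by 4, and nobody above 28 on cognitive FIM can gain 7. Short of those limits, the 3-month score follows baseline with a slope below 1, so patients who start worse tend to change more.

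This would matter little if the two groups started alike, but Table IV shows that they did not. Baseline NIHSS was 6.5 (SD 4.3) in adherers and 4.1 (SD 2.2) in non-adherers; cognitive FIM was 24.1 (6.9) and 28.5 (3.9). Welch tests on these summaries give P=0.013 and P=0.024. Table III points the same way, with an odds ratio for adherence of 14.9 (1.9 to 115.7) for baseline NIHSS of 5 or more. Because patients selected themselves into the adherent group, baseline severity confounds the Table V comparison directly. The NIHSS row is the only significant result in that table, and the table's title ties the improvement to adherence.

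**Working it through.** **1. Reproduce the printed P-values.** Uncorrected Pearson chi-squared, N(ad−bc)² / product of the four margins:
- NIHSS: 49 × (16×16 − 14×3)² / (30×19×19×30) = 49 × 214² / 324,900 = 6.91, P=0.0086 (printed 0.01).
- Cognitive FIM: 34 × (10×9 − 12×3)² / (22×12×13×21) = 34 × 54² / 72,072 = 1.38, P=0.241 (printed 0.24).

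Yates (0.020 and 0.42) and Fisher (0.015 and 0.29) do not match. The printed values are crude chi-squared tests.

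**2. Slope of 3-month score on baseline, from the Table IV SDs.** Correlation r = (SD_base² + SD_3m² − SD_change²) / (2 × SD_base × SD_3m); slope = r × SD_3m / SD_base.
- NIHSS adherent: r = (18.49 + 9.61 − 6.76) / 26.66 = 0.80, slope 0.577.
- NIHSS non-adherent: r = (4.84 + 6.76 − 4.84) / 11.44 = 0.59, slope 0.698.
- NIHSS pooled slope 0.594, residual SD about 1.95.
- Cognitive FIM: slopes 0.200 and 0.393, pooled 0.228, residual SD about 3.0.

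**3. Expected responders if baseline is all that matters.** One common line is applied to both groups, through the overall means (NIHSS 5.569 at baseline, 2.661 at 3 months). Each group keeps its own baseline mean and SD. The simplest version ignores scale limits and assumes normality:
- Adherent: predicted 3-month score 2.661 + 0.594 × (6.5 − 5.569) = 3.21, mean improvement 3.29, SD √[(0.406×4.3)² + 1.95²] = 2.62. P(improvement ≥4) = 1 − Φ(0.27) = 39%.
- Non-adherent: predicted 3-month score 2.661 + 0.594 × (4.1 − 5.569) = 1.79, mean improvement 2.31, SD √[(0.406×2.2)² + 1.95²] = 2.15. P(improvement ≥4) = 1 − Φ(0.79) = 22%.

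**4. Rejection rate.** Each pair of proportions goes into binomial distributions with the Table V group sizes. The probabilities of all outcomes with |z| > 1.96 are then summed, where z is the pooled two-proportion statistic.

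| Variant, no adherence effect given baseline | Expected responders | Gap (points) | Chi-squared rejects |
|---|---|---|---|
| NIHSS, base case: normal baseline, rounded, bounded, pooled line | 44% vs 23% | 21 | 32% |
| NIHSS, unbounded, pooled slope | 39% vs 22% | 18 | 26% |
| NIHSS, unbounded, slope 0.698, cut at 3.5 (lowest) | 45% vs 31% | 14 | 17% |
| NIHSS, bounded, overall rate matched to 19/49, slope 0.577 (highest) | 47% vs 26% | 21 | 34% |
| Cognitive FIM, base case | 58% vs 29% | 30 | 36% |
| Cognitive FIM, unbounded, slope 0.393, cut at 6.5 (lowest) | 61% vs 37% | 24 | 25% |
| Cognitive FIM, bounded, overall rate matched to 13/34, slope 0.200 (highest) | 49% vs 19% | 30 | 41% |

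Gaps were taken before rounding. With equal true proportions in the two groups (39% for NIHSS, 38% for cognitive FIM) the same test rejects 5.2% and 4.7% of the time, so the excess comes from baseline and not from the chi-squared approximation. Nearly all the false rejections favour adherers. Fisher's test gives 12–29% (NIHSS) and 19–31% (cognitive FIM).

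**5. Room to respond.** Under normal or gamma baselines, about 39–46% of non-adherers and 24–27% of adherers start at NIHSS 3 or below. About 50–58% and 26–30% start above 28 on cognitive FIM. The unbounded variants still reject far more than 5% of the time, so excluding patients who cannot reach the cut-off would not remove the bias.

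**6. Baseline-adjusted difference in 3-month score, from the published summaries.**
- NIHSS: (2.7 − 2.6) − 0.594 × (6.5 − 4.1) = −1.33, SE 0.60, P about 0.03.
- Cognitive FIM: (32.4 − 33.1) − 0.228 × (24.1 − 28.5) = +0.30, SE 1.14, P about 0.79.

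**The case against.** **The NIHSS result may be more than baseline.** Table IV already analyses NIHSS change adjusted for baseline NIHSS and gives P=0.03, and step 6 agrees. Under two baseline-only NIHSS models, a P-value as small as the observed one arises in about 8–10% of replicates and a gap as large as 37 points in about 7–8%. A reader might infer from the rejection rates that the NIHSS association is all artefact. The documents do not support that: baseline accounts for only part of the gap, and the adjusted result remains. This objection stands. It also shows how far P=0.01 is from the right reference, since 8–10% is about ten times the nominal 0.0086.

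**No false positive was reported for cognitive FIM.** That row has P=0.24, so no significant claim rests on it, and a reader should not infer one. The base case also overpredicts adherent responders (58% against 45% observed). Matching the overall responder rate does not help the crude test, however; the rejection rate rises to 36–41%. The observed 20-point gap is smaller than the 24–30 points that baseline alone predicts.

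**The test and significance level are inferred.** This is correct. The plan does not prespecify chi-squared for Table V, and 0.05 is assumed. Fisher's test lowers the rates but leaves them well above 5%.

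**Table V is secondary.** The primary endpoint is CPAP adherence, which this does not touch, and Table V is a dichotomised companion to Table IV. This bears on severity and is accepted.

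**Conclusion.** The point holds at moderate severity. Table V compares crude proportions in self-selected groups that differed at baseline on the very scales being dichotomised. With no adherence effect given baseline, the crude test would reject roughly 17–34% of the time for NIHSS and 25–41% for cognitive FIM. Baseline alone would produce about 17–21 of the 37 NIHSS points (about 14 in the mildest variant).

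These figures rest on a common straight line for both groups, assumed normal or gamma baselines, a two-sided 0.05 level, and slopes derived from rounded SDs. Only means and SDs are published, so the ends of the ranges can move by a few points with choices such as the residual SD. No variant comes near 5%.

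The conclusion is limited to Table V: its NIHSS P=0.01 overstates the evidence. The Table IV value of 0.03 is the better guide to the strength of that association, and because adherence was self-selected, neither value is causal. The cognitive FIM row gives no sign of an adherence effect beyond baseline.

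**What to change.** - Replace the two Table V tests with logistic regressions of response on adherence plus that scale's own baseline score: NIHSS for the NIHSS row, cognitive FIM for the cognitive FIM row. Baseline NIHSS should not stand in for baseline cognitive FIM.
- Use a small-sample method such as Firth's penalised likelihood, because each row has only 3 non-adherent responders (19 and 13 responders in all).
- Report the adjusted odds ratio with its 95% CI beside the raw counts.
- Label the raw proportions unadjusted and descriptive, and draw no conclusion from their P-values.

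Both baseline scores are already collected, so the cost is two small models and a revised table. The downside is that the adjusted estimates will be imprecise and the NIHSS contrast will look less favourable than 53% against 16%.

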Official title: Maximizing Use of Continuous Positive Airway Pressure in Stroke Rehabilitation Patients With Obstructive Sleep Apnea

NCT number: 02809430

Document date: March 10, 2019

Design: Single-arm, open-label study

Objectives: To assess the effectiveness of a multifaceted and intensive adherence program on 3month CPAP adherence and measures of stroke outcome (NIH stroke scale and Functional Independence Measure) among stroke patients undergoing inpatient rehabilitation (IPR)

Methods:

Eligible stroke patients (Table I) were enrolled and trialed auto-adjusting CPAP (4–20 cm H2 O; Dream Station, Philips Respironics) over a 3-night run-in period during IPR. Devices were interrogated for nightly usage, average pressure, and a residual apnea-hypopnea index (the respiratory events per hour of sleep). At the end of the run-in period, evidence of OSA was determined based on airflow resistance detected by the machine (see diagnosis of OSA below). Patients with evidence of OSA were eligible for CPAP treatment during IPR and after discharge from IPR. Nurses, respiratory therapists, sleep technologists, and clinical psychologists initiated the SCOUTS intensive CPAP adherence protocol during IPR emphasizing early CPAP tolerance, individual motivation (Table II) and support throughout the treatment period. The primary end point was CPAP adherence over 90 days from CPAP initiation, defined as \geq 4 hours of use on \geq 70% of days. Secondary efficacy end points were changes in the motor and cognitive components of the Functional Independence Measure (FIM) between admission and 3 to 4 months after discharge from IPR and in the National Institutes of Health Stroke Scale (NIHSS) between enrollment and 90 days.

Diagnosis of obstructive sleep apnea (OSA)

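### Motor FIM, a named secondary end point with no difference shown, is left out of the responder analysis without a reason, and Table V's title claims an association for cognitive FIM that its own test does not show

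*Combined protocol and SAP*

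**What the plan says.** The Methods section gives three secondary outcomes. It says "Secondary efficacy end points were changes in the motor and cognitive components of the Functional Independence Measure (FIM" and adds change in NIHSS in the same sentence. Nothing ranks motor FIM below the other two.

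The Statistical Analyses section then describes three steps:

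- **Unadjusted comparison.** This covers all three outcomes: differences "in NIHSS, motor FIM and cognitive FIM by CPAP adherence using the t-test with unequal variances (Table IV").
- **Adjusted regression.** The text names two: "We also evaluated for association of CPAP adherence with 3-month NIHSS and cognitive FIM change using linear regression". Table IV nevertheless prints an adjusted P for motor FIM. The end of that row reads "30.2 (13.2) 0.83 0.65": non-adherent mean change (SD), unadjusted P, adjusted P. The footnote describes the adjusted P-values as "adjusted for age, sex, body mass index, race and baseline NIHSS using linear regression" and makes no exception for motor FIM.
- **Responder comparison.** The text says "we evaluated the proportion of adherent and non-adherent participants who had improvement in the cognitive FIM and NIHSS". The cut-offs, ≥7 for cognitive FIM and ≥4 for NIHSS, are described as exceeding the mean improvement in the whole sample. No motor FIM cut-off is given.

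The last table is headed "Table V. Improvement in cognitive FIM and NIHSS associated with CPAP adherence". Table IV carries the same title wording, although it has a motor FIM row.

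**The concern.** Table IV has two outcomes with P<0.05 and one without, and the responder analysis takes forward only the two. A reader who turns to Table V cannot tell that a third secondary end point exists. Its title also asserts an association for both rows, when one of them has P=0.24.

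There is a related weakness. The cut-off values depend on the observed sample mean, so they could be fixed only after the data were in. The Statistical Analyses section labels the added aphasia models as post hoc but gives the responder analysis no such label.

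What is at stake is how consistent the secondary evidence appears. Three outcomes in two tables make six cells. Three show P<0.05 (cognitive FIM and NIHSS in Table IV, NIHSS in Table V), two do not (motor FIM in Table IV, cognitive FIM in Table V), and one is absent (motor FIM in Table V). The primary end point is not affected.

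**Working it through.** **Inputs.** Table IV, mean change (SD), adherent v non-adherent:

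- motor FIM 31.2 (15.7) v 30.2 (13.2), n=22 and 12
- cognitive FIM 8.2 (6.5) v 4.6 (3.0), n=22 and 12
- NIHSS -3.8 (2.6) v -1.6 (2.2), n=30 and 19

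Table V: cognitive FIM responders 10/22 v 3/12; NIHSS responders 16/30 v 3/19.

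**Step 1: reproduce the printed unadjusted P-values.** Welch t-test from the printed summaries, with each mean and SD varied by ±0.05 for rounding:

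| Outcome | Recomputed P | Rounding range | Printed |
|---|---|---|---|
| Motor FIM | 0.845 | 0.829 to 0.861 | 0.83 |
| Cognitive FIM | 0.035 | 0.029 to 0.042 | 0.03 |
| NIHSS | 0.0028 | 0.0015 to 0.0049 | 0.003 |

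All agree within rounding. The adjusted P-values need patient data and cannot be checked.

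**Step 2: precision of the motor FIM result.** SE = √(15.7²/22 + 13.2²/12) = √(11.20 + 14.52) = 5.07, with Welch df 26.3 and t = 2.054. Difference 31.2 − 30.2 = 1.0; 95% CI 1.0 ± 10.4, or -9.4 to 11.4.

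**Step 3: reproduce Table V.** Pearson chi-squared without continuity correction.

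- Cognitive FIM: 34 × (10×9 − 12×3)² / (22×12×13×21) = 99,144 / 72,072 = 1.38, P=0.241 (printed 0.24). Risk difference 45.5% − 25.0% = 20.5 points; Wald 95% CI -11.7 to 52.6.
- NIHSS: 49 × (16×16 − 14×3)² / (30×19×19×30) = 2,244,004 / 324,900 = 6.91, P=0.0086 (printed 0.01).

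**Step 4: test the cut-off rule.** Whole-sample mean improvement, weighted from Table IV:

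- cognitive FIM: (22×8.2 + 12×4.6)/34 = 235.6/34 = 6.93
- NIHSS: (30×3.8 + 19×1.6)/49 = 144.4/49 = 2.95
- motor FIM: (22×31.2 + 12×30.2)/34 = 1,048.8/34 = 30.85

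The scores are whole numbers, so improvement above the mean is ≥7, ≥3 and ≥31. The first matches Table V; the second does not, since Table V uses ≥4. Rounding of the printed means does not explain it: at the upper limits, (30×3.85 + 19×1.65)/49 = 146.85/49 = 2.997, still below 3. The other reading, rounding the mean and then requiring a larger value, gives ≥4 for NIHSS but ≥8 for cognitive FIM and ≥32 for motor FIM. Neither reading produces both printed cut-offs.

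**Step 5: what a motor FIM row might show (illustration only).** The counts need patient data. If changes were normal with the Table IV means and SDs, about 51% v 48% would reach 31 points (roughly 11/22 v 6/12, P about 1.0). At 32 points it would be about 48% v 45% (roughly 11/22 v 5/12, P about 0.64).

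**The case against.** The strongest answer is that motor FIM is not hidden. Table IV gives its means, SDs, group sizes and both P-values. A reader might infer from the regression sentence that every further analysis was confined to the favourable outcomes. The documents do not support that: the adjusted motor FIM result, P=0.65, is in the table. For the regression this is a mismatch between text and table, not a withheld analysis. This part of the answer stands in full.

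A reader might also infer that the responder outcomes were chosen because of their results. The documents do not say when or why they were chosen, so the pattern is consistent with selection but does not show it. Table V also prints an unfavourable result for cognitive FIM, so it is not uniformly positive.

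Further, the named end points are mean changes. Nothing requires each to be dichotomised as well, and splitting a 1.0-point difference at a cut-off would add little information. That is fair as to content. It does not explain why one of three end points of equal standing was left out.

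Finally, adding a motor FIM row means adding another data-derived cut-off, and ≥31 is not settled because the printed cut-offs do not follow one rule. This stands, and it is why the rule has to be reconciled before the row is added.

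**Conclusion.** The concern holds for the responder analysis and the table titles. Motor FIM is omitted from Table V without a reason, and the outcomes retained are exactly those nominally significant in Table IV. Table V's title asserts an association for cognitive FIM that its own test does not show (20.5 points, 95% CI -11.7 to 52.6, P=0.24).

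The motor FIM result should be read as no association shown. It is not evidence of no effect, because the interval of -9.4 to 11.4 points is wide.

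The NIHSS cut-off of ≥4 does not follow from the stated rule if the whole sample means the 49 patients in Table IV. The document does not define it otherwise. Whether the NIHSS responder result (P=0.01) would change at ≥3 cannot be determined without patient data.

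The intervals and weighted means assume that the printed means, SDs and counts are correct to rounding. The consequence is limited to the presentation of secondary analyses, but correcting it changes what Table V can be said to show.

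**What to change.** 1. State one cut-off rule and apply it identically to all three outcomes. Reconcile it first with the NIHSS cut-off, or explain which sample gave a mean that leads to ≥4. Then add the motor FIM row to Table V. From the Table IV means, exceeding the mean gives ≥7, ≥3 and ≥31 for cognitive FIM, NIHSS and motor FIM.
2. Label the responder analysis post hoc, because its cut-offs come from the observed sample mean.
3. Add motor FIM to the regression sentence in Statistical Analyses so that it matches Table IV.
4. Retitle Tables IV and V neutrally, for example: motor FIM, cognitive FIM and NIHSS by CPAP adherence. The document has no conclusion section. Wherever results are summarised, say that no association was shown for motor FIM and that the cognitive FIM responder comparison was not significant.

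The cost is one extra row from data already held, a recount of NIHSS responders if that cut-off changes, and some wording. The summary becomes less uniformly positive.

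### The NIHSS responder cut-off of ≥4 does not follow from the plan's own rule, which gives ≥3 on the Table IV means; the non-adherent NIHSS row of Table IV also disagrees with itself

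*Combined protocol and SAP*

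**What the plan says.** The last paragraph of Statistical Analyses sets the responder definition for Table V. A responder's improvement had to be "greater than the mean improvement among the entire sample: ≥ 7 for cognitive FIM improvement and ≥ 4 for NIHSS improvement". The text does not say which patients make up the entire sample.

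Table IV gives the group means from which that whole-sample mean can be rebuilt. Its NIHSS footnote reads "n=30 adherent group and n=19 non-adherent" and its FIM footnote "n=22 adherent group and n=12 non-adherent". Table V carries the same two group sizes. Table IV prints an NIHSS change of -3.8 (SD 2.6) for adherent patients and -1.6 (SD 2.2) for non-adherent patients. The non-adherent means are 4.1 at baseline and 2.6 at 3 months.

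Table V reports 16 of 30 (53%) against 3 of 19 (16%) for NIHSS improvement of at least 4, P=0.01. For cognitive FIM improvement of at least 7 it reports 10 of 22 (45%) against 3 of 12 (25%), P=0.24.

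**The concern.** A mean NIHSS improvement of 3.8 in 30 patients and 1.6 in 19 averages to slightly under 3. The smallest whole-point improvement above such a mean is 3, yet the plan uses 4. The cut-off is then stricter than its stated rationale, and it moves every patient who improved by exactly 3 points from responder to non-responder.

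The cut-off defines the one Table V row with P below 0.05. A threshold that departs from its own rule in that row needs either correction or a stated reason.

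The source row raises a second doubt. In the non-adherent group 4.1 minus 2.6 is 1.5, while the printed change is 1.6. The whole-sample mean lies close to 3, so the row that feeds it has to be right.

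**Working it through.** **Assumption.** Both scales are scored in whole points. The Efficacy Measures section gives only the range and direction ("NIHSS; range, 0 to 42; higher scores indicate greater neurologic impairment").

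**1. The cut-off the plan's rule does reproduce (cognitive FIM).** Whole-sample mean = (n₁m₁ + n₂m₂)/(n₁ + n₂) = (22×8.2 + 12×4.6)/34 = 235.6/34 = 6.93. Whole-point totals that round to the printed means are 180–181 and 55, so the mean lies between 6.91 and 6.94. The smallest whole number above it is 7, as stated.

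**2. The same rule for NIHSS.**

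| Source in Table IV | Whole-sample mean | Whole-point totals (adherent + non-adherent) | Range of mean |
|---|---|---|---|
| Change column | (30×3.8 + 19×1.6)/49 = 144.4/49 = 2.95 | 113–115 + 30–31 = 143–146 | 2.92–2.98 |
| Baseline minus 3-month | (30×3.8 + 19×1.5)/49 = 142.5/49 = 2.91 | 112–116 + 27–29 = 139–145 | 2.84–2.96 |

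A mean of 3.00 needs 147 points. Neither column reaches it, so the smallest whole number above the mean is 3. Even without the whole-point assumption, both printed changes at the top of their rounding intervals give (30×3.85 + 19×1.65)/49 = 146.85/49 = 2.997.

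**3. The non-adherent NIHSS row (n=19).**
- Baseline 4.1: total 77 or 78.
- 3 months 2.6: total 49 or 50.
- Improvement from these: 77−50 = 27 up to 78−49 = 29, that is 1.42 to 1.53 per patient.
- Printed change 1.6: needs a total of 30 or 31.

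The two ranges do not overlap. The other five group rows pass the same check:

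| Row | Total from baseline and 3-month means | Total from printed change |
|---|---|---|
| NIHSS, adherent | 112–116 | 113–115 |
| Cognitive FIM, adherent | 181–183 | 180–181 |
| Cognitive FIM, non-adherent | 55 | 55 |
| Motor FIM, adherent | 685–688 | 686–687 |
| Motor FIM, non-adherent | 362–363 | 362–363 |

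The row discrepancy hardly touches Table IV's own test, which was "unadjusted using t-test with unequal variances". The standard error is √(2.6²/30 + 2.2²/19) = 0.693. A difference of 2.2 gives t=3.18 and P=0.0028; a difference of 2.3 gives t=3.32 and P=0.0018. The printed value is 0.003. It fits -1.6, but with rounding a total of 29 could also give it, so it does not show which mean is wrong.

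**4. What a recount could do.** The uncorrected chi-square test reproduces both Table V values: 0.241 for cognitive FIM (printed 0.24) and 0.0086 for NIHSS (printed 0.01; Fisher 0.015). Moving to ≥3 adds the patients at exactly 3, whose number is not reported. Illustrations, not bounds:

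| At exactly 3: adherent, non-adherent | Responders | Chi-square P | Fisher P |
|---|---|---|---|
| 6, 2 | 22/30 vs 5/19 | 0.001 | – |
| 4, 2 | 20/30 vs 5/19 | 0.006 | – |
| 4, 3 | 20/30 vs 6/19 | 0.016 | 0.021 |
| 4, 4 | 20/30 vs 7/19 | 0.041 | 0.076 |
| 2, 3 | 18/30 vs 6/19 | 0.052 | 0.079 |
| 0, 2 | 16/30 vs 5/19 | 0.063 | 0.081 |
| 4, 5 | 20/30 vs 8/19 | 0.090 | – |

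A search over whole-point changes that match the printed change means, SDs and ≥4 counts (also allowing a non-adherent total of 29) leaves 0 to 13 adherent and 0 to 9 non-adherent patients at exactly 3. Over those combinations the chi-square P runs from below 0.001 to 0.99. The summaries do not fix even the direction of the effect.

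**The case against.** **The entire sample may not be these 49 patients.** Patients were enrolled before the run-in that settled OSA status, and NIHSS "scores were obtained in-person on enrollment and at 90 ± 7 days from enrollment". A wider set is conceivable and the margin is thin: added to a change-column total of 143 to 146, one more patient who improved by 4 to 7 points would bring the total to 150 over 50 patients. The mean would then be 3.00 and the rule would give ≥4. What stands is that the population must be stated. But the documents show no other set with 3-month NIHSS, and Table V uses the same 30 and 19.

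**The mean may have been rounded first.** A mean rounded to 3, then strictly exceeded, gives ≥4. Cognitive FIM would then round to 7 and need ≥8, but the plan uses ≥7. The exact mean gives 7 and 3, and the rounded mean gives 8 and 4. Neither reading yields the printed pair, and the exact mean is the literal reading.

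**The row discrepancy may be rounding.** With continuous scores, 4.1, 2.6 and 1.6 are compatible, because the intervals overlap between 1.55 and 1.60. The contradiction does need whole-point scores and the same 19 patients in all three columns. The footnote supports the second condition and the first is an assumption. The cut-off finding does not depend on this row: the mean is 2.95 with a change of -1.6 and 2.91 with -1.5.

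**The consequence is small.** This stands. The primary endpoint and the Table IV comparisons of mean change do not use the cut-off.

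**Conclusion.** The concern holds. On the 49 patients of Table IV the stated rule gives an NIHSS cut-off of ≥3, one point below the one used, while it gives the stated ≥7 for cognitive FIM. The shortfall is narrow: 147 points are needed for ≥4, against at most 146 from the change column and 145 from the baseline and 3-month columns. The non-adherent NIHSS row of Table IV is internally inconsistent by at least one point in total (at most 29 against at least 30).

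The conclusion rests on whole-point scoring and on the entire sample being the patients shown in Tables IV and V. The effect on the 16/30 versus 3/19 contrast is unknown until the patients at exactly 3 are counted. Table V is supportive, so this should be fixed, but it does not threaten the main analyses.

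**What to change.** 1. Check the non-adherent NIHSS row of Table IV against the patient data, correct whichever mean or n is wrong, and rerun that row's tests if the change moves.
2. In Statistical Analyses, state the whole-sample mean NIHSS improvement to two decimals and name the patients it covers.
3. Recount the NIHSS row of Table V at ≥3, as the stated rule gives, and report the new counts and P-value with the name of the test.
4. Keep ≥4 only as a sensitivity cut-off, labelled as such, with the reason it was chosen.

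The cost is one table check and one recount from existing data. The price may be a less favourable contrast in the only Table V row with P below 0.05, although it could also become stronger.
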